## 2.7 SITE SELECTION CRITERIA

As defined in the ISO 14155, prior to the initiation of the clinical investigation, the qualifications of the Principal Investigator and adequacy of the investigation site shall be verified and documented.

Sites must have adequate facilities and equipment to treat/evaluate the patients. The investigational staff must have adequate experience, commitment to safety and consistency in adherence to the protocol. For each enrolled patient, the IP' safety/performance evaluations will be monitored until the End Of Study Visit.

The Principal Investigator must understand and agree to this Protocol. The Principal Investigator and the study Sponsor (or its designee) will execute a clinical trial agreement. The investigational site is also required to execute said clinical trial agreement.

Statement addressing the financing of the clinical investigation, including a description of the agreement between the Sponsor and investigation site(s), will be available in a separated document.

## 2.8 SCREENING FAILURES

Subjects who will fail to meet the inclusion and exclusion criteria are defined as screening failures. Principal Investigator will maintain a Screen Failure Log for screening failures. The log will document at minimum the Subject number and the reason(s) for excluding the Subject from the study. This log will be kept as a source document in the Investigator's Study File. It will be used to determine systematic bias in selection of Subjects for entry into the study.

## 2.9 SUBJECT WITHDRAWAL AND DISCONTINUATION/STOPPING OF TREATMENT

All Subjects are expected to continue in the "CS-BCL-EU2021" study except in the event of death or upon a Subject's early withdrawal from the clinical study. Although every Subject is informed of her right to withdraw at any time from the clinical study, all measures should be taken by the Investigator to encourage Subjects to return for required follow-up visits. If a large number of Subjects are lost to follow-up, attaining clinical study objectives could be jeopardized. The Investigator may prematurely discontinue or withdraw any Subject from the study if any of the study procedures are deemed potentially harmful to the Subject.

Once a Subject has been enrolled in the study, she may withdraw her consent to participate in the study at any time without prejudice. Participation in this clinical investigation is entirely voluntary.

Any Subject receiving breast surgery with BCL who prematurely terminates participation, will undergo a final examination (end-of-study visit/early termination visit). For Subjects considered lost to follow-up, the eCRF will be completed up to the last visit.

The Investigator has the right to terminate participation of any Subject at any time if he/she deems it in the Subject's best interest. The discontinuation from the study may be foreseen in the following (but not limited to) conditions:

	Study Title	An Interventional, Post-Market Study to Evaluate the Performance of a Custom-made Medical Device, "Breast Cancer Locator Guidance (BCL)" System, in Breast-conserving Surgery (BCS)		
	Study ID	CS-BCL-EU2021	Sponsor	CairnSurgical Inc.
	Date	25Nov2022	Version	1.0 Substantial Amendment 1_GERMANY

- Subject withdraws consent for personal reasons;
- Significant non-compliance with study protocol or lack of cooperation;
- Pre-existing violation of eligibility criteria;
- Serious Adverse Event (SAE) or concomitant illness developed by the subject, which, in the opinion of the Investigator and/or the medical expert, does not recommend continuation in the trial;
- Concomitant assumption of prohibited products/medications during the study;
- Subject lost to follow-up;
- Other reasons as determined by the Investigator.

If a Subject is withdrawn, the Sponsor (or its designee monitor) should be informed as soon as possible (i.e., no later than 24 h after learning of the event).

## 2.10 STUDY PROCEDURES AND VISITS

### 2.10.1 Visit Scheduling

Following the evaluation of the inclusion/exclusion criteria and after signing the Informed Consent Form (ICF) criteria at the screening visit (V0), four additional visits will be planned.

At visit 1 (V1), the Subject will undergo *supine* MRI (10-40 days before surgery), from which the 3D breast image and BCL will be made.

At visit 2 (V2) the patient will undergo BCS using the BCL System. On the same day, the specimen volume will be determined. The excised specimen will be sent to the pathological lab for analysis. The surgeon will be asked to fill a 5-point Likert scale to express the ease of use of the BCL.

At visit 3 (V3), follow-up assessments (including physical examination, and AEs review) will be performed.

At the End Of Study (EOS/V4), AEs events will be assessed and patients will be asked to express their satisfaction with the BREAST-Q.

AEs, and concomitant medications, will be assessed from V0 until the EOS visit. Vital signs will be measured from V0 until V3. Any device deficiency/incident will be recorded at V1 and V2.

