No devices will be utilized to assess whether cancer cells may be present at the edges of the specimen or the lumpectomy cavity. Frozen section pathologic analysis of specimen margins will not be utilized. Additional shave biopsies may be taken after the initial tumor resection at the discretion of the Investigators. To minimize potential Investigator bias, additional shave biopsies can only be taken if the following criteria are met: 1) the Investigator palpates a margin of the specimen or the lumpectomy cavity which is suspicious for cancer or 2) the specimen mammogram indicates that the cancer is < 2 mm from a margin. If the Investigator decides to remove additional margins because of

	Study Title	An Interventional, Post-Market Study to Evaluate the Performance of a Custom-made Medical Device, "Breast Cancer Locator Guidance (BCL)" System, in Breast-conserving Surgery (BCS)		
	Study ID	CS-BCL-EU2021	Sponsor	CairnSurgical Inc.
	Date	25Nov2022	Version	1.0 Substantial Amendment 1_GERMANY

findings on specimen palpation or specimen mammography, the number of additional specimens will be recorded, their volume will be determined by water displacement, and they will be marked for margin orientation.

The Investigator should specifically request that Pathologist evaluates and records the distance from the invasive cancer (and separately, if present, from DCIS) to all 6 tumor edges. The consensus guidelines will be used to define positive margins (see **APPENDIX 1**).

To evaluate the surgeon's perception of ease of use of the BCL System, the Investigator will complete a 5-point Likert scale. If, for any reason, the PI is not able to fill the 5-point Likert Scale soon after surgery, the procedure must be completed prior discharge of the patient.

At **visit 2 (V2; Prior to discharge)**, the patient (including the surgical site) will be examined. Post-operative pain medications will be prescribed as per standard of care. The study Investigator will review adverse events and concomitant medications. Device deficiencies/incidents will be monitored.

At **visit 3 (V3; Follow-up)**, Subjects will be seen on-site for a post-operative evaluation. Subjects will have vital signs taken and a physical exam consisting of evaluation of the surgical site. A review of adverse events will also be performed.

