#### **Laboratory examinations:**

##### Pathological analysis

Soon after surgery, tumor specimen handling is either performed directly by the surgeon (PI) or by the PI's delegate. In either case the PI oversees and is responsible for the process.

The tumor specimen will be analyzed locally, at hospital by the Investigator or designee. In details:

- the specimen volume will be determined on the same day of surgery;
- the specimen mammogram will be obtained on the same day of surgery;
- the positive margin rate (PMR) will be obtained within 14 days from the day of sample arrival at the Pathology laboratory.

Once the tumor specimen arrives at the Pathology laboratory:

- specimen surfaces are inked by the surgeon with different colors for orientation,
- the Pathologist performs microscopic evaluation of the margin status, measuring the distance from the edges of the tumor to the edges of the specimen.

See **APPENDIX 1** for additional information about the PMR.

	Study Title	An Interventional, Post-Market Study to Evaluate the Performance of a Custom-made Medical Device, "Breast Cancer Locator Guidance (BCL)" System, in Breast-conserving Surgery (BCS)		
	Study ID	CS-BCL-EU2021	Sponsor	CairnSurgical Inc.
	Date	25Nov2022	Version	1.0 Substantial Amendment 1_GERMANY

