#### 2.11.5 Steps That Will Be Taken To Control Or Mitigate The Risks

The risks associated with the BCL System will be minimized by the clinical investigation design as follows:

- a) Risk of allergy or severe adverse reaction to gadolinium based intravenous contrast. All Subjects will have already undergone a standard of care *prone* contrast-enhanced MRI prior to study enrollment. Any Subject who had an allergic or severe adverse reaction to gadolinium will be excluded from this study.
- b) Risk of nephrogenic sclerosis secondary to gadolinium. Nephrogenic Systemic Fibrosis (NSF) risk appears highest for patients with chronic, severe kidney disease (GFR < 30 mL/min/1.73m^2) as well as patients with acute kidney injury. The risk appears lower for patients with chronic, moderate kidney disease (GFR 30 to 59 mL/min/1.73m^2) and little, if any, for patients with chronic, mild kidney disease (GFR 60 to 89 mL/min/1.73m^2). This complication is extremely rare in Subjects with normal renal function. Subjects with impaired renal function (GFRs <30 mL/min/1.73 m^2) will be excluded from this study.
- c) Risk of infection due to the BCL. Any adverse event will be monitored during the study.
- d) The risk of pneumothorax from needles inserted using the BCL will be monitored during the study.
- e) The risk of inaccurate localization using the BCL, resulting in either missing the tumor or having a higher-than-expected positive margin rate, will be monitored during the study.

Furthermore, a list of warnings/precautions are reported on the IFU related to each kit.

Considering the design of the study, to collect the safety data, vital signs, physical examination will be assessed during the study. During scheduled visits, Subjects will be properly interviewed by Investigator or delegates to assess the adherence to the indications and protocol procedures, as well as to evaluate any adverse event or Concomitant Medication intake.

During the performance of all the procedures required and described in this protocol, the Principal Investigator and the involved collaborators will give high priority to the health and the well-being of each enrolled Subject until the end of the study.

	Study Title	An Interventional, Post-Market Study to Evaluate the Performance of a Custom-made Medical Device, "Breast Cancer Locator Guidance (BCL)" System, in Breast-conserving Surgery (BCS)		

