### 3.7 ADVERSE EVENT REPORTING

Timely and complete reporting of Adverse Events (AE) and safety assessments allows:

- Protection of safety and study Subjects;
- Greater understanding of the overall safety profile of the study treatment;
- Appropriate modification of study protocols and improvement in study design and procedures;
- Adherence to regulatory requirements;

The definitions and reporting requirements adopted in this study are derived from the current International standard on clinical investigations: ISO 14155:2020 and MDCG 2020-10.

Adverse event, adverse device effect and device deficiency/incident information will be collected throughout the study. The investigator or its delegates will record these events on the CRF. The event, date of onset, severity, duration, and relationship to the device will be recorded. Any adverse event will be monitored until it is adequately resolved or explained.

	Study Title	An Interventional, Post-Market Study to Evaluate the Performance of a Custom-made Medical Device, "Breast Cancer Locator Guidance (BCL)" System, in Breast-conserving Surgery (BCS)		
	Study ID	CS-BCL-EU2021	Sponsor	CairnSurgical Inc.
	Date	25Nov2022	Version	1.0 Substantial Amendment 1_GERMANY

The Investigator or its delegates will monitor the occurrence of adverse events for each Subject, including lead-in Subjects, during the course of the study. All Adverse Events (AEs) reported by the Subject, observed by the Investigator, or documented in medical records will be recorded on the adverse event CRF, whether believed by the Investigator to be related or unrelated to the investigational device. Starting with the study enrollment, any new event/experience that was not present at baseline, or worsening of an event present at baseline, is considered an adverse event. All adverse events and unanticipated adverse device effects will be collected and monitored throughout the entire course of the study.

Unchanged, chronic conditions are not adverse events and should not be recorded on the adverse event CRF.

If AE will persist after EOS visit, the Principal Investigator will be in touch with the Subject to support the best decision ensuring the safety/wellbeing of trial Subjects.

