### 3.10 DEVICE DEFICIENCIES REPORTING TO SPONSOR AND EC

According to ISO 14155:2020, a device deficiency is any inadequacy of a medical device with respect to its identity, quality, durability, reliability, usability, safety or performance. Device deficiencies include malfunctions, use errors, and inadequacy in the information supplied by the manufacturer including labelling. This definition includes device deficiencies related to the investigational medical device or the comparator (if applicable).

All device deficiencies of an investigational device shall be documented throughout the clinical investigation and managed by the Sponsor in accordance with written procedures for the control of a non-conforming product. The Sponsor shall take, where applicable, appropriate corrective and preventive actions to protect the safety of subjects, users, and other persons. Device deficiencies of the comparator, if applicable, shall be documented.

The Sponsor shall arrange for the safe return of the investigational device that is related to the device deficiency. Device deficiencies that did not lead to an adverse event but could have led to a serious adverse device effect

- a) if either suitable action had not been taken,
- b) if intervention had not been made, or
- c) if circumstances had been less fortunate,

shall be reported. Where applicable, the analysis of used investigational devices shall be included as supportive information.

The Sponsor is responsible for review all device deficiencies and determine and document in writing whether they could have led to a serious adverse device effect; in case of disagreement between the Sponsor and the Principal Investigator, the Sponsor shall communicate both opinions to concerned parties.

All device deficiencies that could have led to a serious adverse device effect will be reported to the Sponsor without unjustified delay (according to the indications reported in *Section 3.8*) and reported to the EC and the regulatory authority, as required by local law.

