### 3.12 INCIDENTS

Incident means any malfunction or deterioration in the characteristics or performance of a device, including use-error due to ergonomic features, as well as any inadequacy in the information supplied by the manufacturer and any undesirable side-effect.

Incidents in medical devices may arise due to:

- shortcomings in the design or manufacture of the device itself
- inadequate instructions for use
- inadequate servicing and maintenance
- locally initiated modifications or adjustments
- inappropriate user practice
- inappropriate management procedures
- inappropriate environment in which a device is used or stored
- selection of the incorrect device for the purpose

Serious incident means any incident that directly or indirectly led, might have led or might lead to any of the following: (a) the death of a patient, user or other person, (b) the temporary or permanent serious deterioration of a patient's, user's or other person's state of health, (c) a serious public health threat.

The Principal Investigator should report to the Sponsor all incidents or suspected incidents using the contact details reported in *Section 3.8* without unjustified delay (e.g. within 24 hours).

The reporting of the incidents will be performed according to the requirements of the Regulation EU 2017/745 (MDR), and Manufacturer's Standard Operating Procedures.

The Manufacturer will report incidents to the Competent Authority (CA) complying with the following timings, in accordance with MEDDEV 2.12-1 rev. 8 (Guidelines on a Medical Devices Vigilance System):

- Serious public health threat: immediately, but not later than 2 calendar days after awareness of this threat;
- Death or unanticipated serious deterioration in state of health: immediately after establishing a link between the device and the event but not later than 10 calendar days following the date of awareness of the event;
- Others: immediately after establishing a link between the device and the event but not later than 30 elapsed calendar days following the date of awareness of the event.

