##### Collected Variables:

- Any DEVICE DEFICIENCIES occurred during IP utilization? [CRF –V1, V2]
- If Yes, please clarify the reason (free text) [CRF –V1, V2]

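### The schedule and SAP record device deficiencies only at V1 and V2, against Protocol 3.7 and 3.10, so one recognised later has no specified route into the deficiency table

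*Protocol*

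**What the plan says.** Two groups of provisions give different collection periods.

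**Schedule and analysis**
- Protocol 2.10.1: "Any device deficiency/incident will be recorded at V1 and V2".
- The Protocol 2.10.3 flowchart marks the deficiency/incident row under V1 and the V2 surgery column. The prior-to-discharge, V3 and V4 columns are blank.
- The visit lists in Protocol 2.10.5 to 2.10.8 match: the item appears for V1 and for surgery, but not before discharge, at V3 or at V4.
- The SAP 1.2.5 flowchart has the same pattern. The source question in SAP 6.4.5 is "Any DEVICE DEFICIENCIES occurred during IP utilization? [CRF –V1, V2", with a free-text follow-up from the same pages. It feeds a by-visit table and a listing in the safety set.

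**Safety provisions**
- Protocol 3.7: "Adverse event, adverse device effect and device deficiency/incident information will be collected throughout the study". It adds that these events are recorded on the CRF.
- Protocol 3.10: "All device deficiencies of an investigational device shall be documented throughout the clinical investigation".
- Protocol 3.12: "The Principal Investigator should report to the Sponsor all incidents or suspected incidents", with no limit by visit.
- Protocol 2.10.2, describing V2 before discharge: "Device deficiencies/incidents will be monitored".

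**The concern.** The study aims to confirm the safety and performance of a new custom-made device, and the deficiency table is one of the places where a reader will look for that. Protocol 3.10 defines a deficiency broadly: inadequate performance, use errors and inadequate labelling all count. Some of these can come to light only after the operation. On histology, Protocol 2.10.2 says "the positive margin rate (PMR) will be obtained within 14 days from the day of sample arrival at the Pathology laboratory", which will usually be after the day of surgery. Protocol 2.11.5 names a device risk that histology bears on: "The risk of inaccurate localization using the BCL, resulting in either missing the tumor or having a higher-than-expected positive margin rate" is to be monitored during the study.

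If no form asks about deficiencies after surgery, a low count in the table could reflect when the question was asked as well as how the device behaved.

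**Working it through.** The plan gives no figure on this point, so there is none to reproduce. The check sets the provisions side by side, works out the uncovered period and follows each kind of late finding to where it would be reported.

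**1. Collection point by point**
- V1: scheduled in the protocol and the SAP.
- V2, surgery: scheduled in the protocol and the SAP.
- V2, before discharge: monitored according to the 2.10.2 text, but absent from the 2.10.3 flowchart, the 2.10.6 pre-discharge list and the SAP flowchart. The SAP field is tied to the V2 page as a whole.
- V3, V4 and between visits: required by 3.7 and 3.10, but with no scheduled item and no SAP field.

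**2. Uncovered period** (visit windows from the flowchart)
- V3: 14 ± 7 days, so day 7 to day 21 after surgery.
- V4: 42 ± 7 days, so day 35 to day 49 after surgery.
- Pathology: up to 14 days after the specimen reaches the laboratory. Assuming it arrives on the day of surgery, the report may come as late as day 14. An early V3 (day 7) can precede it.
- Protocol 4.11 asks for eCRF entry within 5 working days of each visit, so the V2 page can be due before the pathology report exists.

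**3. Where a finding recognised after V2 would go**
- It caused an adverse event: the cumulative adverse event form, collected to V4 with relationship to the device, and the SAP adverse event tables.
- It is a positive margin: the V2 page (SAP 6.2.1) and the primary table. That page therefore does take a result that arrives later.
- It is an incident: reported to the sponsor under 3.12. The SAP has no incident table.
- It is a deficiency without an adverse event: 3.10 requires documentation, and reporting where it could have led to a serious adverse device effect. The SAP names no field for it outside the V1 and V2 pages, and no text tells the investigator to reopen the V2 answer.

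The last case is the gap. Adverse event collection does not close it, because Protocol 3.10 expressly covers deficiencies that led to no adverse event.

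**4. Does margin status stand in for localization?**
Not reliably. In the pilot described in Protocol 2.11.1, 18 of 19 cancers were accurately localized, so 1 was not, yet all 19 patients had negative margins. The SAP 6.2.2 histology field for the lumpectomy specimen offers DCIS, IBC or both, with no category for tumour absent. The SAP defines no localization-accuracy variable.

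**The case against.** The strongest defence is that V1 and V2 are the visits at which the device is used. Body contact is limited to less than 24 hours, the form comes off before resection, and the wires are removed at surgery. The specimen radiograph is also taken then and will reveal some misses. Tabulating deficiencies by visit of use is reasonable, and the SAP question refers to the period of use. The margin result shows that the V2 page can take late information, and Protocol 4.10.2 and 4.12 allow audit-trailed corrections. Incidents go to the sponsor at any time, device-related adverse events are collected to V4, and positive margins are the primary endpoint.

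Most of this stands, and it rules out three stronger readings.
- A reader might infer that late deficiencies can never reach the table. The documents do not bar a late entry on the V2 page; they simply do not provide for one.
- A reader might infer that no scheduled form addresses inaccurate localization. Positive margins, one of the two consequences named in 2.11.5, are collected and analysed as the primary endpoint.
- A reader might infer that the deficiency rate is biased downward by a known amount, for instance by applying the pilot's 1 in 19 to 35 patients. That rate comes from palpable tumours, and no inaccurate localization occurred in the 10 patients treated after a design modification. It counts all inaccurate localizations rather than those first recognised after V2. A positive margin alone is also not a deficiency.

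The defence does not remove the conflict with 3.7 and 3.10, or supply a route for a late deficiency without an adverse event. A visit of use and a date of recognition are different things, and the SAP provides only for the first.

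**Conclusion.** The point holds as an internal contradiction with a consequence for the analysis. The schedule and the SAP limit deficiency recording to V1 and V2, while Protocol 3.7 and 3.10 require it throughout. Followed as scheduled, a deficiency recognised after V2 without an adverse event has no specified route into the SAP table or listing, so both may be incomplete.

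The size that can be stated is the period without a scheduled item: from V2 to V4, 35 to 49 days after surgery, covering most or all of the pathology window. The number of deficiencies missed cannot be derived, because the documents give no rate of late recognition.

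The conclusion rests on the protocol text supplied (Version 1.0, Substantial Amendment 1, Germany) and SAP version 0.1. The SAP cites protocol version 2.0 and a version 2.0 CRF, which were not available, and the text of Protocol 3.8 was also not available. A deficiency log in that CRF could narrow the gap, although the SAP's own flowchart and field list still show only V1 and V2.

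**What to change.** 1. In Protocol 2.10.1, the flowchart, the lists in 2.10.6 to 2.10.8 and the CRF, add the deficiency/incident item at V2 before discharge, V3 and V4. Alternatively, use a cumulative log like the adverse event form. Either makes the schedule agree with 3.7, 3.10 and the 2.10.2 text.
2. Have the investigator update the answer once the pathology report is available, at V3 or on receipt if that is later. State that a positive margin alone is not a deficiency, so that the table does not mix a performance outcome with a device inadequacy.
3. In SAP 6.4.5 and the SAP flowchart, replace the V1 and V2 source with all of these entries. Have the table and listing use date of recognition, and add that date and the free-text description to the listing shell, which now shows only patient, visit and yes/no. State whether incidents are tabulated.

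The cost is one yes/no item with free text at visits that already exist, or one log page, plus small edits to the protocol, CRF and SAP. The reported deficiency count may be slightly higher.
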